1.1 Entry Criteria

Each patient eligible for participation in this study must meet the following criteria:

1. Those who voluntarily participated in this study and were able to sign a written informed consent form, and understand and agree to comply with the requirements of this study and the evaluation schedule.

2. The insured is 18–75 years old on the date of signing the informed consent form.

3. In the case of a patient with bladder urothelial carcinoma of cT2-T4aNxM0 based on AJCC Version 8 bladder cancer TNM staging, histologic diagnosis and imaging evaluation, in which the investigator believes there is a residual lesion after the TURBT surgery; Patients with histologically mixed tumors require urothelial carcinoma to dominate (at least 50%).

4. The patient who is intolerant or does not accept cisplatin drug treatment must be determined for the researcher. Patients who are intolerant to cisplatin chemotherapy must meet at least one of the following criteria:

- a. The fitness status of ECOG was > 1;
- b. Creatinine clearance < 60 mL/min;
- c. Hearing loss \geq Grade 2 in the National Cancer Institute Generic Term Standard for Adverse Events (NCI-CTCAE) Version 5;
- d. Peripheral neuropathy Grade 2 or higher in NCI-CTCAE Version 5;
- e. With new york Heart Association Grade III or above heart failure.

5. The investigator assesses that the radical cystectomy needs to be performed after the neoadjuvant treatment, and the indications for radical surgery are met, so the investigator is willing to undergo the surgery.

6. HER2 detection in local laboratory using pre-treatment tumor specimen: HER2 expression confirmed after IHC result (defined as: IHC 1+ 2+ 3+).

7. ECOG physical status 0~1.

8. The patient's organ function was good, as measured by the following screening laboratory values obtained \leq 14 days before enrollment:

A. Patients should not use growth factor support \leq 14 days prior to sample collection when screening for:

I. Absolute neutrophil count $\geq 1.5 \times 10^9/L$;

II. Platelet $\geq 100 \times 10^9/L$;

III. Hemoglobin $\geq 90 g/L$;

B. The international standardized ratio or activated partial thromboplastin time ≤ 1.5 upper limit

of normal (ULN);

- C. Total serum bilirubin $\leq 1.5 \times$ ULN;
- D. AST, ALT and alkaline phosphatase $\leq 2.5 \times$ ULN;
- E. Calculated creatinine clearance is greater than 30 mL/min;

9. Women who are not pregnant or have fertility must be willing to use high-potency contraception during the study and ≥ 120 days after the last dose of vidicon or Ampley mab, whichever occurs later, and have a negative urine or serum pregnancy test result within ≤ 7 days prior to enrollment.

10. The male who is not sterilized must be willing to use efficient contraceptive methods during the study and up to 120 days after the last dose of vidicon or pie Ampley monoclonal antibody (whichever is later).

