Clinical Study Protocol

Protocol Name: A Clinical Study of Disitamab Vedotin for Injection Combined With Penpulimab Injection in Neoadjuvant Therapy for Patients With HER2-expressing Cisplatin-intolerant cT2-T4aNxM0 Bladder Urothelial Carcinoma

Sponsor: Sun Yat-sen Memorial Hospital, Sun Yat-sen University

Version number: V1.0

Version date: 2022.5.1

Signature confirmation of scheme:

Compliance Statement

In compliance with the Provisions of the Good Laboratory Practice Regulations, Administrative Measures for Investigator-initiated Clinical Studies in Medical and Health Institutions (for Trial Implementation) and the Declaration of Helsinki, participants pledged to conduct this study in accordance with this protocol. Participants must be trained to conduct the study after obtaining the written approval of the Ethics Committee and the informed consent of the subjects. Protocol modifications need to be re-approved.

I. programme summary

Project Name: A Clinical Study of Disitamab Vedotin for Injection Combined With Penpulimab Injection in Neoadjuvant Therapy for Patients With HER2-expressing Cisplatin-intolerant cT2-T4aNxM0 Bladder Urothelial Carcinoma

Abbreviation of Scheme: RC48-C039

Test purpose:
 
To evaluate the efficacy and safety of neoadjuvant treatment with Disitamab Vedotin for Injection Combined With Penpulimab Injection in patients with cT2-T4aNxM0 bladder urothelial carcinoma and HER2-expressing cisplatin intolerance.

Test brief:
 
The single-armed, exploratory clinical study of vidicon monoclonal antibody combined with pie Ampley monoclonal antibody designed for cisplatin-intolerant patients with cT2-T4aNxM0 bladder urothelial carcinoma in this study confirmed the effectiveness and safety of the new adjuvant treatment of vidicon monoclonal antibody combined with pie Ampley monoclonal antibody for cisplatin-intolerant patients with cT2-T4aNxM0 bladder urothelial carcinoma, and finally provided new evidence-based evidence for new adjuvant treatment of such patients.

Sample size:
 
This is a prospective clinical study. It is intended to collect 48 patients with cT2-T4aNxM0 bladder urothelial cancer who are HER2-expressing and cisplatin-intolerant, and all of them have received neoadjuvant treatment with vidicon monoclonal antibody in combination with pie Ampley monoclonal antibody.

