In this study, we intended to add immunotherapy to the treatment of patients with locally advanced urothelial carcinoma of the bladder who were intolerant to locally advanced cisplatin, so as to obtain the efficacy and safety indicators for the platinum-intolerant patients with locally advanced urothelial carcinoma of the bladder treated with the neoadjuvant therapy of vidicon combined with Ampley monoclonal antibody, and to provide guidance for the follow-up Phase III clinical trial and clinical application.

III. Study purpose and endpoint

1. Research purposes

1.1 Main research objectives:

To evaluate the pathological complete response rate (pCR rate) after radical cystectomy in patients with HER2 expression, cisplatin-intolerant cT2-T4aNxM0 vesical urothelial carcinoma treated with neoadjuvant therapy of vidicon combined with Ampley monoclonal antibody.

1.2 Secondary study objectives:

A) Evaluating the pathological descending rate;

B) Evaluating event-free survival (EFS);

C) Evaluating overall survival (OS);

D) To evaluate the safety of the new adjuvant therapy and its impact on radical cystectomy (evaluated according to NCI-CTCAE v5 and surgical complications according to Clavien-Dindo scoring criteria).

2. Analysis set:

2.1 Safety analysis set: Includes all patients who received at least 1 dose of any study drug (any component of neoadjuvant combination therapy).

2.2 Effectiveness analysis set: Includes all patients who received at least 1 dose of any study drug treatment (any component of neoadjuvant combination therapy) and had a radical cystectomy following that treatment.

3. Observation indicators

3.1 Main indicators:

Pathological complete response rate (pCR rate): the pathological stage after radical cystectomy was pT0N0 (based on effectiveness analysis)

3.2 Secondary indicators:

A) Pathological decline rate: the proportion of patients with pathological stage \leq pT1N0 (based on the efficacy analysis set) after radical cystectomy;

B) Safety: to evaluate the safety and impact on radical cystectomy of the new adjuvant therapy (evaluated according to NCI-CTCAE v5 and surgical complications according to Clavien-Dindo scoring criteria) (based on the safety analysis set);

C) Event-free survival (EFS): EFS is defined as the time from enrollment to disease progression, death from any cause, or new onset of another tumor.

D) Total survival (OS): Total survival was defined as the time from enrollment to death for any cause.

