3. The investigator judges that the operation timing is delayed, including but not limited to: disease progression occurs in the new adjuvant treatment stage or AE fails to complete 4 cycles of new adjuvant treatment, and the operation is not performed although it is assessed by the investigator to be in line with the indications for radical surgery;
4. Combined use of any anti-tumor therapy;
5. Patients fail to comply.

Patient withdrawal (individual patient ends the study): A patient may withdraw from the study for the following reasons, including but not limited to the following: 1. The patient withdraws informed consent; 2. Death; 3. Loss of follow-up.

V. research design

5.1 overall design

This is a multicenter, open-label, single-arm prospective clinical study to evaluate the efficacy and safety of neoadjuvant treatment with vidicon and Ampley monoclonal antibody in patients with cisplatin-intolerant cT2-T4aNxM0 urothelial carcinoma of the urinary bladder. In the absence of active withdrawal from the trial, intolerable drug-induced toxic and side effects, or findings that the subject was considered by the investigator to be unsuitable for further trials, each subject will undergo post-treatment surgery according to the following protocol, with efficacy evaluation and follow-up at each cycle.

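### Entry criterion 4 also admits patients who decline cisplatin, but the title, objective and design describe the population as cisplatin-intolerant only

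*Protocol*

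**What the plan says.** Section IV, 1.1, criterion 4 has two sentences. The first sets out who may enter: "The patient who is intolerant or does not accept cisplatin drug treatment must be determined for the researcher". The second governs the list a to e (performance status, creatinine clearance, hearing loss, neuropathy, heart failure): "Patients who are intolerant to cisplatin chemotherapy must meet at least one of the following criteria". The list is tied to intolerant patients. Nothing further is asked of a patient who does not accept cisplatin.

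Elsewhere the population is described without the second group:

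- Title: "Neoadjuvant Therapy for Patients With HER2-expressing Cisplatin-intolerant cT2-T4aNxM0 Bladder Urothelial Carcinoma".
- Programme summary, sample size: 48 patients with "cT2-T4aNxM0 bladder urothelial cancer who are HER2-expressing and cisplatin-intolerant".
- Programme summary, test brief: having named cisplatin-intolerant patients, it says the study "finally provided new evidence-based evidence for new adjuvant treatment of such patients".
- Section III, 1.1, main objective: the pCR rate "in patients with HER2 expression, cisplatin-intolerant cT2-T4aNxM0 vesical urothelial carcinoma treated with neoadjuvant therapy".
- Section 5.1, overall design: efficacy and safety "in patients with cisplatin-intolerant cT2-T4aNxM0 urothelial carcinoma of the urinary bladder".

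Sections III.2 and 5.4.2 define the efficacy analysis set by receipt of study drug followed by radical cystectomy, without regard to the reason for entry. Section 5.4.3.1 analyses the primary endpoint on that set.

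**The concern.** A single-arm trial has no control group to absorb a difference between the patients described and the patients treated. The result is one proportion set against a fixed historical rate, so what it means depends on whom it describes. Here the enrolment rule admits two kinds of patient, and the stated question and intended evidence concern one of them. Unless this is reconciled, a pCR rate from a mixed group would be reported as the rate in cisplatin-intolerant patients. The protocol says at the end of Section 2.1 that the result is meant to guide a phase III trial and clinical application, so the label will be carried forward.

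**Working it through.** **1. Is there really a second route?** Criterion 4 joins the two descriptions with *or*, and its second sentence attaches a to e to the first description only. The remaining entry criteria (consent, age, stage and histology, cystectomy indication, HER2, ECOG 0–1, organ function, contraception) and the 17 exclusions do not require cisplatin intolerance. A patient with normal renal function, hearing and nerve function who declines cisplatin can satisfy every criterion.

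**2. Does any statement of the population include that route?** No. The title, test brief, sample-size entry, main objective and overall design name intolerant patients only. The protocol has no section headed Conclusion. The test brief is the nearest statement of the intended conclusion, and it also refers to intolerant patients.

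**3. Does the primary analysis separate the two groups?** As stated in the protocol, no: one pCR rate in one efficacy set. The design figures belong to that pooled rate. For 10% against 25%, one-sided alpha 0.05 and 80% power, the optimal Simon two-stage design has 18 patients in stage 1 and 43 in total (exact alpha 0.048, power 0.800, with cut-offs of 3 and 8). Then 43 / 0.9 = 47.8, giving 48. These sizes match Section 5.4.1. The cut-offs printed there (2 and 7) and the printed null hypothesis of 25% are separate matters and do not affect this point.

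**4. Can the effect on pCR be sized?** Let *f* be the share of decliners in the efficacy set, and p_I and p_D the pCR rates in intolerant and declining patients.

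Pooled rate = (1 − f) × p_I + f × p_D, so pooled rate − p_I = f × (p_D − p_I).

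The protocol gives none of *f*, p_I and p_D separately. Purely as assumptions, take *f* from 0.2 to 0.5 and a gap p_D − p_I of +15, 0 or −15 percentage points:

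| Assumed gap | f = 0.2 | f = 0.5 |
|---|---|---|
| +15 points | 0.2 × 15 = +3.0 | 0.5 × 15 = +7.5 |
| 0 | 0 | 0 |
| −15 points | −3.0 | −7.5 |

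The documents do not favour any row, so neither the sign nor the size can be determined. The mismatch of population exists in all three.

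**5. What would a separate estimate cost in precision?** Take the protocol's expected 25%, with standard error = √(p(1 − p)/n).

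- All 43 patients: √(0.1875/43) = 6.6 points.
- Intolerant patients 80% of the set (assumed): 6.6 / √0.8 = 7.4 points.
- Intolerant patients 50% of the set (assumed): 6.6 / √0.5 = 9.3 points.

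**The case against.** The best reply is that this is only a label. Criterion 4 states the decliner route openly, enrolling such patients is a legitimate choice, and the study calls itself exploratory. The two groups may also differ little. Every patient must be ECOG 0–1 (criterion 7), be a candidate for cystectomy (criterion 5) and have adequate organ function (criterion 8). The documents give no reason why reduced creatinine clearance, hearing loss or neuropathy should alter pathological response to a regimen without cisplatin. A breakdown by entry reason may also sit in a statistical analysis plan that is not at hand, and the English is a rough translation.

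Much of this stands. The lack of a subgroup table in the protocol is not a finding, and admitting decliners is not an error. The translation calls for caution, although two alternatives remain the likeliest reading of the sentence. None of this removes the contradiction within the protocol between whom criterion 4 admits and whom the title and objective describe.

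A reader might go further and infer that fit decliners, being likelier to reach surgery, would inflate the pCR rate. The documents do not support that. Cystectomy is a condition of entering the efficacy set, so a higher surgery rate cannot itself raise the pCR rate among decliners; it can only change their share of the set.

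**Conclusion.** The point holds as an inconsistency of population. Criterion 4 enrols patients who are intolerant of cisplatin or who do not accept it, whereas the title, programme summary, main objective and overall design claim a result for intolerant patients alone. As written, the pooled pCR rate would be attributed to a narrower population than the one that produced it. This rests on reading criterion 4 as two alternatives, with a to e binding only the first.

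The protocol supports no numerical bias. It would also go too far to say that the result would come mainly from decliners, that the false-positive rate is inflated by a known amount, or that the trial cannot answer its question. Each of these needs a share of decliners or a pCR gap that the documents do not give, and the gap may be zero.

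**What to change.** Reconcile criterion 4 with the stated population in one of two ways. Neither requires a change to eligibility, treatment or sample size.

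1. Describe the population as *intolerant of or declining cisplatin* in the title, programme summary, main objective, overall design and eventual conclusion. This costs a wording change only.
2. Keep the present description, but record each patient's entry reason (which of a to e, or declined), report pCR with its confidence interval for patients meeting at least one of a to e, and rest any statement about cisplatin-intolerant patients on that group. The pooled rate can still be reported under its accurate label. The investigator must already establish the entry reason to confirm eligibility, so the extra work is one recorded item and one tabulation. The price is the wider interval for the subset.

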1.2 Exclusions

Patients who met any of the following criteria did not meet the enrollment requirements:

1. Patients who have previously received therapies targeting PD-1, PD-L1, PD-L2, CTLA4, and Her2, or other antibodies or drugs that specifically target T cell co-stimulation or checkpoint channels.

2. Receiving other approved systemic anti-cancer treatments or systemic immunomodulators (including but not limited to interferon, interleukin-2 and tumor necrosis factor) within 28 days before enrollment.

3. Patients who have received radiotherapy for bladder cancer in the past.

4. Patients who have received medical treatments targeting tumors in the past, with the following exceptions:

A. In patients who have previously received systemic chemotherapy, a treatment-free interval of at least 12 months from the last treatment to the start of neoadjuvant therapy;

B. Local intravesical chemotherapy or immunotherapy is completed at least 1 week before initiation of study neoadjuvant therapy.

5. Major surgery has been performed or major trauma has occurred within 28 days before enrollment (implantation of vascular access device and TURBT are not considered as major surgery).

6. Severe infections requiring systemic anti-bacterial, anti-fungal or anti-viral treatment within 14 days prior to enrollment (HBV infection is performed as described in exclusion criterion 12).

7. Live vaccines have been administered within 28 days prior to enrollment (Seasonal influenza vaccines are usually inactivated and are therefore allowed to be administered. Intranasal vaccine is a live vaccine, so it is not allowed to be used).

8. Anyone who has received any Chinese herbal medicine or proprietary Chinese medicine for

the control of cancer within 14 days before enrollment.

9. Active autoimmune diseases requiring systemic treatment that the researchers assess as having an impact on study treatment.

10. The need for long-term use of large amounts of hormones or the use of other immunosuppressive agents, the researchers assessed that there is an impact on the study of treatment.

11. The history of potassium, sodium, calcium abnormalities or hypoalbuminemia, interstitial lung disease, non-infectious pneumonia or other uncontrolled systemic diseases that the investigator believes may affect treatment, including diabetes, hypertension, and cardiovascular diseases (such as active heart diseases including severe/unstable angina, myocardial infarction, symptomatic congestive heart failure and ventricular arrhythmia requiring drug treatment within the six months prior to enrollment), etc.

12. Treatment-naive subjects with chronic hepatitis B or hepatitis B virus (HBV) carriers with HBV DNA \geq 500 IU /mL (2500 copies/mL) were excluded from the study. Note: Patients with inactive hepatitis B surface antigen carriers or stable active HBV infection (HBV DNA $<$ 500 IU/mL [2500 copies /mL]) after continuous antiviral therapy may be enrolled. HBV DNA testing is only performed in patients who are positive for antibodies to hepatitis B surface antigen.

13. patients with active hepatitis c shall not be included in the group. Patients who were negative for HCV antibody during the Screening Period or negative for HCV RNA after a positive HCV antibody test were enrolled. Only patients with positive HCV antibody testing require HCV RNA testing.

14. Has a history of immunodeficiency (including HIV-positive human immunodeficiency virus, and other acquired or congenital immunodeficiency diseases), or a history of allogeneic stem cell transplantation or organ transplantation.

15. allergies to other monoclonal antibodies are known.

16. Known to be allergic to any study drugs or excipients.

17. Concurrently enrolled in another therapeutic clinical study.

1.3 exit criteria

Patient Discontinuation from Study Treatment: The patient has the right to discontinue study treatment at any time and for any reason. In addition, the investigator has the right to schedule the patient to discontinue study treatment at any time. Patients who discontinue study treatment should be followed if possible and the main reasons for discontinuation of study treatment should be documented on an appropriate electronic case report form (eCRF). Patients may discontinue study treatment for the following reasons, including but not limited to:

1. Pregnancy;

2. The investigator judges various medical conditions in which the safety of the patient under continuous treatment may be threatened;
3. The investigator judges that the operation timing is delayed, including but not limited to: disease progression occurs in the new adjuvant treatment stage or AE fails to complete 4 cycles of new adjuvant treatment, and the operation is not performed although it is assessed by the investigator to be in line with the indications for radical surgery;
4. Combined use of any anti-tumor therapy;
5. Patients fail to comply.

Patient withdrawal (individual patient ends the study): A patient may withdraw from the study for the following reasons, including but not limited to the following: 1. The patient withdraws informed consent; 2. Death; 3. Loss of follow-up.

V. research design

5.1 overall design

This is a multicenter, open-label, single-arm prospective clinical study to evaluate the efficacy and safety of neoadjuvant treatment with vidicon and Ampley monoclonal antibody in patients with cisplatin-intolerant cT2-T4aNxM0 urothelial carcinoma of the urinary bladder. In the absence of active withdrawal from the trial, intolerable drug-induced toxic and side effects, or findings that the subject was considered by the investigator to be unsuitable for further trials, each subject will undergo post-treatment surgery according to the following protocol, with efficacy evaluation and follow-up at each cycle.

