5.3.1 Screening

Screening phase assessments will be conducted within 28 days prior to enrollment and patients who agree to participate will sign up for an ICF prior to undergoing any screening procedures. The screening period starts on the first day of the screening procedure. Screening evaluations can be repeated as needed during screening; The investigator will evaluate a patient's eligibility for inclusion based on the latest screening assessments. Standard tests or test results performed ≤ 28 days before informed consent are available for screening assessments and do not require repeat testing unless otherwise specified.

Demographic data and medical history of 5.3.1.1

Demographic data will include date of birth (or age), gender, and race/ethnicity reported by self. Medical history including a variety of clinically significant medical, surgical or cancer history; • Fertility status; And history of drinking and smoking. Radiographic findings prior to enrollment were collected.

Fertility Women and Contraception in 5.3.1.2

Fertility is defined as the ability to conceive physiologically. .

Informed consent and screening records in 5.3.1.3

Written informed consent to voluntarily participate in the study must be obtained prior to performing any study-specific procedures. The ICFs of all enrolled and screened but not enrolled patients will be maintained at the study center. All screening assessments must be completed and reviewed before patients are admitted to the group, confirming that they meet all eligibility criteria.

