5.3.2 Entry

5.3.2.1 Qualification Confirmation

The investigator will evaluate the eligibility of each patient for inclusion. Results of all screening procedures and associated medical history must be obtained before eligibility is established.

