5.3.5 Visit window

All visits during neoadjuvant therapy were to be within the range of -3 to +7 days of the planned date, and postoperative visits were considered to be 14 days, unless otherwise noted. Evaluations scheduled for the day of study treatment dosing (Day 1) per cycle should be completed prior to study treatment infusion/dosing, unless otherwise noted. Laboratory and imaging results should be reviewed prior to dosing. Scheduling a study visit at a protocol-specified time point that is in conflict with a holiday, weekend, or other event/law will allow the visit to be scheduled to the nearest feasible date.

Visit schedule

	sift	Treatment period (one cycle every 21 days)				Drug safety follow-up r	operation		Postoperative follow-up				
		Cycle 1	Cycle 2	Cycle 3	Cycle 4		Preoperative evaluation	Radical resection	1 week	1 month	3 months (EOT)	6, 12, 18, 24 months	9, 15, 21 months
fate (window)	-28 to -1	one	-3 to +7	-3 to +7	-3 to +7	28 after last dose (-3 to +7)	-7 to 0	28 – 42 after the last dose	±3	±7	±14	±14	±14
Informed consent a	X												
Demographic data/ Treatment historyb	X												
Physical examination/vital signs c	X	X	X	X	X	X	X		X	X	X	X	
ECOG assessment	X	X	X	X	X	X	X		X	X	X	X	
Surgical fitness evaluation	X						X						
Electrocardiogram d	X	X	X	X	X	X	X		X	X	X		
Hematology e	X	X	X	X	X	X	X		X	X	X	X	
Serum biochemistry e	X	X	X	X	X	X	X		X	X	X	X	
Urinalysis e	X	X	X	X	X	X	X		X	X	X	X	
Fecal analysise	X			X			X						

Coagulation e	X						X						
Pregnancy testf	X					X	X						
Hepatitis b two half qualitative g	X						X						
Hepatitis c qualitative g	X						X						
Venereal disease (HIV)g	X						X						
Marker screening (HER2 IHC)	X												
Thyroid functionh	X						X						
Chest CT plain scan i	X			X		X	X				X	X	
Total abdominal+pelvic CT plain scan+enhanced i	X			X		X	X				X	X	
Bladder (or pelvis) Multiparameter mri	X			X			X						
Bone scan i	X												
Previous/concomitant medications	X	X	X	X	X	X	X	X	X	X			
Adverse eventj	X	X	X	X	X	X	X	X	X	X	X		
Vidicon monoclonal antibody administration k		X	X	X	X								
Ampley monoclonal antibody administration l		X	X	X	X								
Radical resection and pathological evaluation m								X					
Archived/fresh tumor histon	X							X					
EQ-5D-5L/ EORTC QLQ-C30 o	X	X	X	X	X	X	X	X	X	X	X	X	
Living condition	X	X	X	X	X	X	X	X	X	X	X	X	X

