F. A urine pregnancy test will be performed on all fertile females. A weakly positive urine pregnancy test must be confirmed by an additional serum pregnancy test.

G serological tests including HBV/HCV/HIV (HBV halves, HCV antibodies, HIV antibodies) will be performed in the local laboratory. HBV DNA testing needs to be added if HbsAg is positive. Additional HCV RNA testing is required if HCV antibodies are positive.

H. In addition to the screening period and preoperative evaluation, the investigator determines whether a thyroid function test is required if clinically indicated.

I. Imaging examinations have been taken under standard treatment before obtaining the written informed consent, and the collection

time is within 28 days before inclusion. If the results meet the clinical requirements and are qualified, no repeated examination is required, but the multi-parameter MRI of bladder (pelvis) after TURBT must be guaranteed. All measurable and evaluable lesions need to be evaluated and documented at the screening visit. Chest, abdomen and pelvis-containing plain CT scan (enhancement at the discretion of the investigator if necessary) and multi-parameter MRI of bladder (pelvis) were selected for imaging examination (VI-RADS score was conducted when conditions were ripe). For each patient, the same imaging studies were used as far as possible throughout the study. The investigator must review the imaging results prior to the next cycle of dosing. During the follow-up period, imaging examinations were selected according to the pathological response of the patient or local medical guidelines. During the follow-up period, if imaging recurrence or metastasis occurs, no imaging examination will be conducted during the follow-up period covered by this study. Craniocerebral examinations and bone scans are required when symptoms appear, if clinically indicated.

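### Exclusion 12 ties HBV DNA testing to surface antibody, while the visit schedule ties it to surface antigen

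*Protocol*

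**What the plan says.** Exclusion 12 in Section IV, 1.2 sets the hepatitis B rule in three parts.

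- The main clause excludes "Treatment-naive subjects with chronic hepatitis B or hepatitis B virus (HBV) carriers with HBV DNA" at or above 500 IU/mL (given there as 2500 copies/mL).
- The note allows enrolment of "Patients with inactive hepatitis B surface antigen carriers or stable active HBV infection", the latter with HBV DNA below 500 IU/mL after continuous antiviral therapy.
- The last sentence says who gets the test: "HBV DNA testing is only performed in patients who are positive for antibodies to hepatitis B surface antigen".

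The visit schedule in Section 5.3.5 has a hepatitis B row, "Hepatitis b two half qualitative g", marked at screening and at the preoperative evaluation. The footnote it carries, G, says: "HBV DNA testing needs to be added if HbsAg is positive".

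Exclusion 6, on severe infections, refers the reader to exclusion 12: "HBV infection is performed as described in exclusion criterion 12". No other eligibility criterion sets an HBV DNA limit.

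**The concern.** The two instructions name different serological markers as the trigger for the same test. Exclusion 12 uses the antibody to the surface antigen; footnote G uses the antigen itself. The people for whom exclusion 12 needs a DNA result are carriers, and its own note identifies them by the antigen.

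What is at stake is safety screening before treatment with a PD-1 antibody and an antibody-drug conjugate. A site that followed the last sentence of exclusion 12 to the letter would have no HBV DNA value for an antigen-positive, antibody-negative patient, and so could not tell whether that patient was above or below the limit. The protocol lists five centres and has the serology done in local laboratories, so each site would have to settle the conflict for itself.

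**Working it through.** No arithmetic applies and the plan gives no figure to reproduce. The check is to apply both rules to every combination of antigen and antibody status.

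Rules as written:

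- Exclusion 12, last sentence: test only if the antibody is positive.
- Section 5.3.5, footnote G: test if the antigen is positive; silent otherwise.

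| Antigen (HBsAg) | Antibody | Exclusion 12 | Footnote G | Action that satisfies both |
|---|---|---|---|---|
| + | + | test allowed | test required | test |
| + | − | no test | test required | none |
| − | + | test allowed | silent | either |
| − | − | no test | silent | no test |

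One of the four patterns, antigen-positive and antibody-negative, has no compliant action. In the third row the rules also differ in emphasis, since exclusion 12 names these patients as the tested group and footnote G does not ask for the test, but a site can meet both.

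Next, exclusion 12 against itself. Its main clause and note both turn on an HBV DNA value in people with chronic infection or carriage. Its last sentence withholds that value from carriers who lack the antibody. For them the criterion cannot be applied as written.

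Hepatitis C serves as a comparison. Exclusion 13 and footnote G agree: HCV RNA follows a positive HCV antibody. The mismatch is therefore confined to the HBV sentence and is not a general difference between the eligibility section and the schedule.

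**The case against.** Four points can be made on the other side.

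First, this is very likely a translation slip. The English text is rough throughout, and the hepatitis B panel alone is rendered in several odd ways. Sites may have worked from a source text without the error. This is plausible but cannot be confirmed from the document, and the sentence stands in the protocol under review.

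Second, the intended rule can be recovered. Footnote G states it, and the carrier wording in exclusion 12 points the same way. Section 5.3.1.3 adds that "All screening assessments must be completed and reviewed before patients are admitted to the group, confirming that they meet all eligibility criteria", and Section 5.3.2.1 that "Results of all screening procedures and associated medical history must be obtained before eligibility is established". This stands and makes the practical risk small, although neither section says which trigger governs.

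Third, the word *only* need not be a ban. The parallel hepatitis C sentence in exclusion 13 limits when the RNA test is required and does not forbid it otherwise. Read that way, a site could test under footnote G without breaching exclusion 12. This is fair, and it softens the second row of the table from a prohibition to a disagreement about whether the test is needed. The eligibility criterion would still name the wrong marker.

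Fourth, harm requires a site to follow one sentence literally, overlook the footnote, and leave the limit unchecked in a patient known to be antigen-positive. That is true, and it is why the point ranks low.

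**Conclusion.** The inconsistency is real and minor. Exclusion 12 and footnote G give different triggers for HBV DNA testing. On the literal reading they are incompatible for antigen-positive, antibody-negative patients and for no other pattern; on the softer reading of *only*, they still disagree about when the test is needed.

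The protocol gives no HBV prevalence, so no count or proportion of affected patients is claimed. The hypotheses, error rates, sample size, stopping rule and pCR analysis are all unaffected.

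That the antigen was meant is an inference from footnote G and from the carrier wording in exclusion 12. The existence of the mismatch does not depend on that inference; the choice of correction does.

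**What to change.** Replace the last sentence of exclusion 12 with: *HBV DNA testing is performed in patients who are positive for hepatitis B surface antigen (HBsAg).* This matches footnote G and the criterion's own reference to surface antigen carriers, and it leaves the limit of 500 IU/mL as it is.

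The cost is one sentence. The hepatitis B panel is already scheduled at screening and at the preoperative evaluation, and footnote G already adds HBV DNA for antigen-positive patients, so no test, visit or sample is added. If the original-language protocol already refers to the antigen, only the English text needs correcting.
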